5.3 IMPUTATION AND ROUNDING RULES

5.3.1 *Missing values*

As culture is only done for positive qPCR values, missing culture results with a qPCR value 'not detected', will be considered as zero (log10).

	Statistical Analysis Plan	
FLU010	Final analysis	Final 3.0 of 15JUN2020

For the calculation of AUCs, the following rules will be used to impute missing values:

- Intermittent missing values will be interpolated. This is implicitly done when using the linear trapezoidal rule.
- In case of trailing missing values, a triangle will be calculated to estimate the area between the timepoint of the last non missing value and the last scheduled assessment, which will be assumed to have a zero value.
- In case of leading missing values, a triangle will be calculated to estimate the area between the first non missing assessment and the first scheduled assessment, which will be assumed to have a zero value.
- In case of trailing missing values with no assessment datetime, the last scheduled assessment datetime will be imputed with challenge datetime + 10 days + 12 hours (for viral load) or + 11 days (SSC)
- In case of leading missing values with no assessment datetime, the first scheduled assessment datetime will be imputed with challenge datetime – 1 min + 1 day (viral load) or with challenge datetime – 1 min (SSC)

Overall/Local/General SSC score will only be calculated if sufficient signs and symptoms are available for each body system: 3/4 nose; 1/2 throat; 2/3 eyes; 2/3 chest/respiratory; 3/4 gastrointestinal and 8/12 body/systemic. Symptoms that are questioned if at least 2 other symptoms with grade 2 or higher are present should only be considered as missing if the condition is met and no value is available.

In case percentage of missing data exceeds 5% for qPCR viral load or for overall SSC, a sensitivity analysis will be done for the AUC based endpoints by using a placebo-based multiple imputation which assumes that all missing viral load concentrations/signs and symptom scores are missing not at random (MNAR). This approach can be considered conservative as subjects from the active treatment arm would adopt the outcome model estimated from the placebo arm.

For the safety analysis, no imputation will be done of missing values (i.e. observed cases analysis).

5.3.2 *Handling partially or completely missing datetimes in calculations*

Partially missing datetime of event will be imputed as follows for the calculation of AUC:

- Missing time will be imputed with challenge time - 5 min for morning samples and challenge time + 12 h for evening samples.
- Missing date will be imputed based on the scheduled timepoint: missing date on Day 3 = challenge date + 2 days

Partially missing date of event will be imputed as follows for the calculation of time to start and time to peak of viral shedding:

- Missing time will be imputed with challenge time - 5 min for morning samples and challenge time + 12 h for evening samples.
- Missing day will be imputed with 1
- Missing day and month will be imputed with 01JAN

	Statistical Analysis Plan	
FLU010	Final analysis	Final 3.0 of 15JUN2020

Partially missing date of event will be imputed as follows for the calculation of time to cessation of viral shedding:

- Missing time will be imputed with challenge time - 5 min for morning samples and challenge time + 12 h for evening samples.
- Missing day will be imputed with last day of the month
- Missing day and month will be imputed with 31DEC

Partially missing start and stop dates of events will be imputed as follows for the calculation of duration of viral shedding:

- Missing time will be imputed with challenge time - 5 min for morning samples and challenge time + 12 h for evening samples.
- Missing start day will be imputed with 1
- Missing start day and month will be imputed with 01JAN
- Missing stop day will be imputed with last day of the month
- Missing stop day and month will be imputed with 31DEC

Note: If imputation of the start date results in a start date posterior to the stop date / anterior to challenge, the start date will be imputed with the stop date / challenge date respectively. If imputation of the stop date results in a stop date anterior to the start date / posterior to date of last contact, the stop date will be imputed with the start date / date of last contact respectively.

5.3.3 *Values below or above a threshold*

Safety values expressed as below (or above) the detection limit will be imputed by the value of the detection limit itself. Listings will always show the non-imputed values.

Viral load values reported as $> XX$ will be imputed with XX . Viral load values reported as $< XX$ will be imputed with $XX/\sqrt{2}$. For values reported as 'not detected', the \log_{10} viral load will be imputed with 0.

Immunogenicity values reported as $> XX$ will be imputed with XX . Immunogenicity values reported as $< XX$ will be imputed with $XX/2$.

5.3.4 *Rounding of derived variables*

Derived variables will be rounded to the appropriate number of significant digits (see Definition of terms) at ADaM level:

- Age and BMI will be rounded to 1 decimal
- Log-transformed values will not be rounded.
- vAUC will be rounded to integer
- SSC score (and peak) and SSC AUC will be rounded to 2 decimals
- Time to and duration variables will be rounded to 1 decimal

All derivations will be done before rounding. Rounding will be done using the round half to even tie-breaking rule (see Definition of terms).

	Statistical Analysis Plan	
FLU010	Final analysis	Final 3.0 of 15JUN2020

5.3.5 *Outliers*

There will be no outlier detection. All measured values will be included in the analyses.

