7.1.2.1 VACCINATION

Vaccination - Day 1

Participants will attend the clinic for Vaccination on Day 1 at least 6 weeks before inoculation and challenge. This visit will also include a review of inclusion/exclusion criteria, blood draws for PBMCs, Serum and Transcriptomics, alcohol breath test, urine drug screen and urine pregnancy test.

Participants will then be vaccinated with either MVA-NP+M1 or saline Placebo depending on the randomization schedule. Following vaccination participants will remain in the clinic for at least 2 hours for monitoring. During this time diary cards will be dispensed and explained for completion over the following 7 days for solicited and unsolicited events and throughout the study for unsolicited adverse events.

Day 2

A blood draw for transcriptomics will be taken in the 24 (± 3) hours post-vaccination. Participants will return to the clinic for safety assessments and transcriptomic blood draw.

Day 4

3 days after vaccination, participants will be contacted by phone as a reminder to complete their diary cards.

Day 8 and Day 28

7 and 27 days after vaccination participants will attend the clinic for follow-up assessments as per the Time and Events Schedule, primarily to assess safety and collect blood for immunogenicity assessments.

Day 56

Participants will be called to be assessed for potential intercurrent ILI and possible date of challenge. The decision whether to exclude the participant will be at the discretion of the Investigator.

7.1.2.2 *CHALLENGE****Day -2 and Day -1***

On Day -2, participants will be admitted to the Clinical Pharmacology Unit (CPU). Eligibility of the participants will be confirmed along with the Assessments listed as per Time and Events Schedule.

Should the participant present a positive Qualitative PCR pre-challenge, the participant will be excluded from this challenge group but may enter any of the subsequent challenge groups if the infection is cleared. The participant excluded at Day -2 from the challenge period may be replaced with a participant with the same treatment on Day -1.

Day 1

On Day 1, assessments will be performed as indicated in the Time and Events Schedule.

After the safety assessments, the participants will be inoculated with challenge virus H3N2 by a trained health care worker, followed by repeated blood sampling and NP swab samples as outlined in the Time and Events Schedule.

Day 2 to Day 11

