2. EFFICACY AND IMMUNOGENICITY ANALYSES

2.1 EFFICACY

2.1.1 *Available data*

Nasal swabs for influenza virus are collected twice a day (at least 8 hours apart) from Day 2 to Day 10 following intranasal challenge, which are tested for influenza using quantitative polymerase chain reaction (qPCR) and culture. Culture is only done for positive qPCR samples.

The following symptoms of influenza-related infection will be collected twice a day (except for lymphadenopathy, which will be collected once a day only) from Day 1 to Day 11 of challenge on a symptom score card (SSC):

- Local symptoms:
 - Nose (4): nasal congestion (blocked nose), runny nose, sneezing frequency, sinus pressure/pain or facial pain
 - Throat (2): sore throat, difficulty swallowing
 - Eyes (3): tearful/watery eyes, painful eyes, aversion to light
 - Chest/respiratory (3): dry cough, productive (wet) cough, difficulty breathing/tight chest
- General symptoms:
 - Gastrointestinal (4): nausea, stomach ache, vomiting, diarrhoea
 - Body/systemic (12): dizziness, head congestion, headache, muscle aches, feverish, chills or shivering, lack of appetite, felt cold, sweating, tiredness/weakness, sleeping more than usual, lymphadenopathy
 - The following symptoms will only be questions if at least 2 other symptoms with grade 2 or higher are present: nausea, stomach ache, vomiting, diarrhoea, tiredness/weakness, sleeping more than usual.

Each symptom's severity is graded from 0 (absent) to 3 (grade 3 - severe).

Additionally, the SSC also contains the question whether the subject feels well enough to go to work today (yes/no).

Oral body temperature is assessed daily during confinement as part of the vital signs evaluation. During this same period, tissue collection is planned daily to measure daily mucus production.

	Statistical Analysis Plan	
FLU010	Final analysis	Final 3.0 of 15JUN2020

2.1.2 *Endpoints and derivation rules*

2.1.2.1 *PRIMARY ENDPOINT*

Primary endpoint is the viral area under the curve (vAUC) based on the qPCR values. AUC will be calculated using the linear trapezoidal rule, by summing all individual trapezoids, which will be calculated as follows:

$$AUC_{t_i-t_{i+1}} = 1/2 * (L_i + L_{i+1}) * (t_{i+1} - t_i).$$

Where:

- L_i is the log-transformed viral load concentration at time point t_i .
- All time points (including unscheduled time points) from day 2 to day 10 will be considered.
- AUC will be calculated in hours, using actual datetimes of qPCR assessments.

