5.2 PHASES AND TIME POINTS

5.2.1 *Phases*

All events and assessments will be allocated to phases.

Phase	Start	End
Screening	Date of signing the ICF, with 00:00 added as time part	Vaccination date(time) – 1 minute
Vaccination	Vaccination date(time)	Challenge date(time) – 1 minute
Challenge	Challenge date(time)	End date of Day 28 post-challenge visit, with 23:59 added as time part
Follow-up	End of challenge phase + 1 minute	Date of last contact, with 23:59 added as time part

Per definition, and for each subject, the last available phase ends on the date of last contact (or the cut-off date for the topline analysis), with 23:59 added as time part.

AEs will be allocated to phases as described in section 3.1.2. All other assessments will be allocated to phases based on the assessment date(time).

In case of (partially) missing date(time) fields which cannot be allocated to a phase based on the available date(time) information, the visit label will be used to allocate to the correct phase. If this is not possible (unscheduled visits or visits on a turning point between phases), assessments will be allocated to the vaccination phase unless the available parts of the assessments start or stop date(time) provide evidence for allocating to the challenge/screening/follow-up phase.

5.2.2 *Baseline and change from baseline*

Baseline will be defined by phase.

The vaccination baseline value is the last available and non-missing value before the first administration of any study drug and will be used for data collected during the vaccination period.

The challenge baseline value is the last available and non-missing value before the administration of challenge inoculation and will be used for data collected during the challenge period.

Change from baseline is defined as follows:

Change from baseline at time point t = value at time point t – baseline value.

	Statistical Analysis Plan	
FLU010	Final analysis	Final 3.0 of 15JUN2020

5.2.3 *Relative day*

Relative days (DY) will be calculated both with respect to the vaccination and to the challenge, according to the following rule:

- Concerned date < reference date: DY = concerned date – reference date
- Concerned date \geq reference date: DY = concerned date – reference date + 1

The reference dates are the vaccination date and the date of challenge.

5.2.4 *Analysis visits*

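### The SAP's trailing-missing rule, used when no datetime is recorded, places the last scheduled assessment 24 hours late and so enlarges the AUC triangle whenever the last value is non-zero

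*SAP*

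**What the plan says.** SAP 5.3.1 closes the AUC after trailing missing values with a triangle. It falls from the last non-missing value to zero at the last scheduled assessment. A separate bullet covers trailing missing values that have no assessment datetime: "the last scheduled assessment datetime will be imputed with challenge datetime + 10 days + 12 hours (for viral load"), or challenge + 11 days for the SSC.

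Other parts of the SAP fix the calendar:

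- Section 5.2.3, for dates on or after the reference date: "DY = concerned date – reference date + 1". The challenge date is therefore Day 1. Protocol 7.1.2.2 agrees, describing Day 1 as follows: "After the safety assessments, the participants will be inoculated with challenge virus H3N2".
- Section 5.3.2, for AUC dates: "missing date on Day 3 = challenge date + 2 days".
- Section 5.3.2, for AUC times: "Missing time will be imputed with challenge time - 5 min for morning samples and challenge time + 12 h for evening samples".
- Section 5.3.1, leading missing values: "the first scheduled assessment datetime will be imputed with challenge datetime" minus 1 minute plus 1 day for viral load, which is Day 2.
- Section 2.1.1: "Nasal swabs for influenza virus are collected twice a day (at least 8 hours apart) from Day 2 to Day 10".
- Section 2.1.2.1, for the primary vAUC: "All time points (including unscheduled time points) from day 2 to day 10 will be considered".

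Footnote 4 to the protocol's Period 2 schedule has the symptom questionnaire given once on Day 11, before discharge. Protocol 3.1 puts discharge on the morning of that day.

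**The concern.** The two ends of one AUC window are imputed on different day counts. The leading rule puts Day 2 at + 1 day, which fits the SAP calendar. The trailing rule puts Day 10 evening at + 10 days + 12 hours, which on that calendar is Day 11 evening: after discharge, with no swab scheduled.

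The rule feeds the primary endpoint. It also feeds culture vAUC and overall SSC AUC, which section 2.1.2.2 derives by the same rules. An affected participant is integrated over a longer window than a completer, and the extra area grows with the last value seen. If affected participants were more frequent in one arm, or had higher last values there, the added area would fall unevenly on the comparison.

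The planned validation need not catch this. Section 1.7 provides independent programming for the primary endpoint tables, but two programmers working from the same text would produce the same anchor. Section 6.3 records no change to the rule in versions 2.0 or 3.0.

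**Working it through.** **Step 1. Time of the last scheduled assessment.** With the challenge at 0 h on Day 1, hours after challenge = (day − 1) × 24, plus 12 for an evening sample.

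| Assessment | On the SAP's calendar | Imputed by 5.3.1 | Difference |
|---|---|---|---|
| First swab, Day 2 AM | 1 × 24 = 24 h | 24 h less 1 min | agrees |
| Last swab, Day 10 PM | 9 × 24 + 12 = 228 h | 10 × 24 + 12 = 252 h | 24 h late |
| Last SSC, Day 11 AM | 10 × 24 = 240 h | 11 × 24 = 264 h | 24 h late |

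Taking the 5-minute morning offset in 5.3.2 literally makes the SSC gap 24 h 5 min. No variant of the anchors that was tried gives 252 h or 264 h.

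**Step 2. Window length.** Viral load: 228 − 24 = 204 h for a completer and 252 − 24 = 228 h under the rule, so 228/204 = 1.118 (+11.8%). SSC: 240 h against 264 h (+10%). These are nominal, because observed swabs enter at their actual datetimes.

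**Step 3. Excess area.** The triangle is ½ × L × (t_end − t_last), where L is the last available value. Moving t_end by 24 h adds ½ × L × 24 = 12 × L. For the SSC, L is the last score. If L = 0, nothing is added.

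**Step 4. Size for one participant.** The last values below are assumed. For the whole vAUC, the observed part is taken as a mean log10 of 3 to 5 times the observed hours from Day 2 AM. This range is also assumed, since the documents give no viral-load figures.

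| Last value | Triangle to 228 h | Triangle to 252 h | Triangle change | Whole vAUC to 228 h (mean 3; mean 5) | Whole vAUC change |
|---|---|---|---|---|---|
| 5 at Day 6 PM (132 h) | ½ × 5 × 96 = 240 | ½ × 5 × 120 = 300 | +60 (+25%) | 3 × 108 + 240 = 564; 5 × 108 + 240 = 780 | 10.6%; 7.7% |
| 3 at Day 8 PM (180 h) | ½ × 3 × 48 = 72 | ½ × 3 × 72 = 108 | +36 (+50%) | 3 × 156 + 72 = 540; 5 × 156 + 72 = 852 | 6.7%; 4.2% |
| 2 at Day 10 AM (216 h) | ½ × 2 × 12 = 12 | ½ × 2 × 36 = 36 | +24 (×3) | 3 × 192 + 12 = 588; 5 × 192 + 12 = 972 | 4.1%; 2.5% |

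**Step 5. Second assumed course.** Let log10 load rise from 0 at Day 2 AM to 6 at Day 4 AM, then fall linearly to zero.

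- Clearance at Day 10 PM: the full vAUC is ½ × 6 × 204 = 612. With the last swab at Day 5 PM (108 h, value 4.62), the rule gives 667 and the 228 h anchor gives 612 (+9.0%). With the last swab at Day 9 PM (204 h, value 0.92), it is 623 against 612 (+1.8%).
- Clearance at Day 8 PM: the full vAUC is ½ × 6 × 156 = 468. With the last swab at Day 5 PM (value 4), the rule gives 612 and the 228 h anchor gives 564 (+8.5%). Once the last value is zero, both give 468.

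**The case against.** No passage justifies a later end point, so the 24 h discrepancy stands. The case on the other side concerns reach and consequence, and much of it holds.

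- **Scope.** A reader might infer that everyone with trailing missing values gets an inflated AUC. The text does not support that. The faulty anchor applies only where no assessment datetime exists; a swab with a recorded time but no result is closed at its own time. Section 5.3.3 sets a result of not detected to log10 = 0, and then the triangle is zero.
- **Competing rule.** Section 5.3.2 dates a missing AUC record from its scheduled time point. A scheduled Day 10 evening record could be placed at 228 h under that rule and at 252 h under 5.3.1. This limits the reach of the error, but it also means the same missing swab can give two different areas.
- **Magnitude.** The +25%, +50% and ×3 figures describe the closing triangle alone, not the endpoint.
- **Meaning of too large.** The comparison is with the same triangle ending on schedule, not with the unobserved true AUC. In the early-clearance course above, even the 228 h anchor (564) exceeds the full area (468).
- **Supporting analyses.** Leaving quarantine early removes a participant from the per-protocol set, on which the primary analysis is repeated if that set differs from ITT. If more than 5% of qPCR values are missing, a placebo-based multiple imputation is added. Either could help expose a result driven by this rule; neither corrects the ITT figure.
- **SSC.** SAP 2.1.1 describes symptom collection twice a day through Day 11. If a Day 11 evening score existed, the SSC anchor would be 264 − 252 = 12 h late instead of 24 h. The protocol footnote and the morning discharge rule this out.

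**Conclusion.** Wrong as written, with severity below must-fix. The one-day slip follows from the SAP's own calendar and needs no outside assumption. Its consequence is bounded: 12 h × the last log10 value (or last SSC score), only for participants with trailing missing values, no datetime and a non-zero last value. The figure of roughly 2–11% of whole vAUC rests on the assumed viral courses above.

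A reader might go further and infer that the primary comparison is biased between arms. The documents do not support that. They give no count of affected participants, no split by arm and no spread for vAUC. The primary test uses ranks, so its response to these shifts cannot be computed. The effect is probably small unless early departures are common or differ by arm.

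**What to change.** In SAP 5.3.1, change the imputed last scheduled datetime to challenge datetime + 9 days + 12 hours for viral load and + 10 days for the SSC. If a later end point was intended, say so and give the reason. State also whether 5.3.1 or 5.3.2 governs a scheduled record with no datetime.

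Then count, by arm, the participants to whom the trailing rule applies and those among them with a non-zero last value. Re-derive qPCR vAUC, culture vAUC and SSC AUC for them. If the count is zero, only the text needs correcting. The cost is a line or two of SAP text, one line of derivation code and, if anyone is affected, a re-run of the AUC displays.

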- AUC will be rounded as detailed in section 5.3.4.
- Missing values will be imputed as detailed in section 5.3.1.

2.1.2.2 *SECONDARY ENDPOINTS*

The following secondary endpoints will be derived:

- Attack rate: a successful attack is defined as having at least two positive swabs (derived for both qPCR and culture) within the timespan of two consecutive days
- Time to start of viral shedding (hours) = (datetime of first of two positive swabs within 2 consecutive days - challenge datetime)/(60*60)
 - Time will be rounded as detailed in section 5.3.4
 - All time points (including unscheduled time points) from day 2 to day 10 will be considered.
 - Subjects not having at least two positive swabs (within 2 consecutive days) will be censored on the last viral load assessment
 - This endpoint will be derived for both qPCR and culture
- Peak viral shedding = highest viral load concentration
 - All time points (including unscheduled time points) from day 2 to day 10 will be considered.
 - Subjects not having at least two positive swabs (within 2 consecutive days) will be excluded from this analysis (peak viral shedding not calculated).
 - This endpoint will be derived for both qPCR and culture

	Statistical Analysis Plan	
FLU010	Final analysis	Final 3.0 of 15JUN2020

- Time to peak of viral shedding (hours) = (datetime of highest viral load concentration - challenge datetime)/(60*60)
 - Time will be rounded as detailed in section 5.3.4
 - All time points (including unscheduled time points) from day 2 to day 10 will be considered.
 - In case of identical peak values, the first in time will be considered.
 - Subjects not having at least two positive swabs (within 2 consecutive days) will be censored on the last viral load assessment
 - This endpoint will be derived for both qPCR and culture
- Time to cessation of viral shedding (hours) = (datetime of first negative swab following the last positive swab - challenge datetime)/(60*60)
 - Time will be rounded as detailed in section 5.3.4
 - All time points (including unscheduled time points) from day 2 to day 10 will be considered.
 - Subjects not having at least two positive swabs (within 2 consecutive days) will be excluded from this analysis (time to cessation not calculated).
 - An event is defined as having two consecutive negative swabs not followed by a positive swab. Subjects without an event will be censored on the last viral load assessment.
 - This endpoint will be derived for both qPCR and culture

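### SAP 5.3.2 dates a swab with a missing date by study day for vAUC but by the first or last day of the month for shedding times, usually outside Day 2 to Day 10

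*SAP*

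**What the plan says.** SAP 5.3.2 gives four lists of rules for partially missing swab datetimes.

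- **AUC:** "Missing date will be imputed based on the scheduled timepoint: missing date on Day 3 = challenge date + 2 days".
- **Time to start and time to peak:** the list opens "Partially missing date of event will be imputed as follows for the calculation of time to start and time to peak of viral shedding", then "Missing day will be imputed with 1" and "Missing day and month will be imputed with 01JAN".
- **Time to cessation:** "Missing day will be imputed with last day of the month" and "Missing day and month will be imputed with 31DEC".
- **Duration:** "Missing start day will be imputed with 1" for the start, and the last-day rule for the stop.

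The rule for a missing clock time is the same in all four lists and differs only between morning and evening samples.

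A closing Note resets a start that falls before challenge to the challenge date, and a stop that falls after last contact to the date of last contact. It also keeps start and stop in order. It follows the duration list and speaks of start and stop dates. Whether it also governs time to start, peak and cessation is not stated.

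SAP 2.1.1 has swabs taken twice a day from Day 2 to Day 10. SAP 2.1.2.2 limits the shedding endpoints to that window: "All time points (including unscheduled time points) from day 2 to day 10 will be considered". These endpoints are derived for both qPCR and culture.

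**The concern.** One swab can carry different dates in different endpoints of the same participant, and no reason is given for dropping the scheduled day outside AUC. The calendar rules are also not needed. The participant is in confinement, the clock-time rule already presumes that the nominal morning or evening sample is known, and finding the first of two positives within two consecutive days already requires the study day.

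When a calendar rule fires, a start or peak will usually land on or before the challenge date, although the first swab is on Day 2. A cessation will usually land after Day 10, when no further swab is taken. Such values would pass directly into the summaries: SAP 2.1.4.1 reports duration with descriptive statistics, SAP 5.4.1 adds a confidence interval on the mean and an arithmetic mean for survival estimates, and SAP 5.3.5 plans no outlier detection.

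**Working it through.** **Inputs from the documents.** Relative day = date − challenge date + 1 (SAP 5.2.3). Swabs on Day 2 to 10 (SAP 2.1.1). Imputation rules and Note (SAP 5.3.2). Last contact is the later of 27 ± 3 days post-challenge and 180 ± 14 days post-vaccination (Protocol 7.1). Challenge at least 6 weeks after vaccination.

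**Assumed.** Only the day of the month is missing. Challenge dates are every day from 15 May 2019 to 8 February 2020 (270 dates). Clock offsets are ignored.

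**1. The SAP's own example.** Challenge date + 2 days gives relative day 2 + 1 = 3, so its Day 3 example is right.

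**2. One participant.** Assume challenge on 10 September 2019, first positive on Day 3 (12 September), peak on Day 5, and first negative after the last positive on Day 8 (17 September).

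| Endpoint | Scheduled day | Calendar rule, Note applied | Calendar rule, Note not applied |
|---|---|---|---|
| Time to start | 2 × 24 = 48 h | 0 h | −9 × 24 = −216 h |
| Time to peak | 4 × 24 = 96 h | 0 h | −216 h |
| Time to cessation | 7 × 24 = 168 h | 20 × 24 = 480 h (Day 21) | 480 h |
| Duration, both days missing | 168 − 48 = 120 h | 480 h | 29 × 24 = 696 h |

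If the month is missing too, 1 January gives −6048 h (0 h with the Note). 31 December gives 2688 h, or 27 × 24 = 648 h with the Note if last contact is Day 28.

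**3. All swab days.** There are 270 × 9 = 2,430 combinations of challenge date and swab day. The first-of-month rule puts 2,025 of them outside Day 2 to 10: 2,025/2,430 = 83.3%. The last-of-month rule also gives 2,025. Either rule hits the true day in 81/2,430 = 3.3%. Applying the Note leaves the share outside the window unchanged, because a reset start lands on Day 1 and a capped stop lands on the day of last contact. For challenge dates from 15 May to 15 December 2019 only, the share is 83.7%.

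**4. Starts on Day 3 or 4.** 270 × 2 = 540 cases. The imputed date is on or before challenge in 495: 495/540 = 91.7%. With the Note applied, the errors sum to −1,269 days: −1,269/540 = −2.35 days, on true values of 2 to 3 days.

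**5. Cessations on Day 7, 8 or 9.** 270 × 3 = 810 cases. The imputed date is after Day 10 in 729: 729/810 = 90%.

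- Last contact on Day 28: mean shift 10,623/810 = 13.1 days, maximum 28 − 7 = 21.
- Last contact late enough not to bind: mean shift 11,970/810 = 14.8 days, maximum 31 − 1 = 30.

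The second case is realistic. A participant challenged at 6 weeks has the six-month contact 180 − 42 = 138 days after challenge.

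**6. Sensitivity to the calendar.** SAP 4.6.1 describes 8 challenge cohorts at 3-week intervals. With 8 such dates, starting on 15 May or up to 59 days later, the 92% ranges from 75% to 100% and the 90% from 71% to 100%.

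**7. Effect on a mean.** The example duration is 480 − 120 = 360 h too long. One such participant moves an arm mean by 360/54 = 6.7 h in placebo or 360/80 = 4.5 h in vaccine, and by more once participants without two positive swabs are excluded.

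**The case against.** The strongest reply is that the rule may never fire. Swabs are taken in confinement, data not on paper go directly into an electronic source system (Protocol 12.3), and cleaning checks and queries follow (Protocol 12.6). A missing clock time is the likelier gap, and that rule is the same everywhere. This stands: the documents do not say how often a date is incomplete.

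Second, the affected endpoints carry limited weight. Protocol 2.3 lists them as exploratory, though Protocol 2.2 and SAP 2.1.2.2 also place them among the secondary endpoints. Duration has no test, p-values are unadjusted in a proof-of-concept study, and a log-rank test responds little to one or two misplaced times. This also stands, and is why the effect is mainly on means.

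Third, earliest start and latest stop is a wide-bounds convention fixed in advance. That would be a reason where the true date is unknown. Here the study day is known, and the SAP uses it for AUC.

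Four stronger readings are tempting, and the documents do not support them:

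- A reader might infer that every imputed time is impossible. About 17% fall inside Day 2 to 10, when the swab window crosses a month boundary.
- A reader might infer that negative times will be analysed. That happens only if the Note does not reach time to start and peak, which is unstated.
- A reader might infer that the treatment comparison is biased in one direction. The same rules apply to both arms, and no differential missingness is shown.
- A reader might infer that the rules were carried over from adverse event dating. No passage says so, and SAP 3.1.2 allocates incomplete adverse event dates to phases without a first-of-month rule.

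**Conclusion.** The inconsistency is real and stands in the text of SAP 5.3.2: whenever a calendar rule fires, it usually gives a wrong date. With only the day missing, about 83% of imputed dates fall outside Day 2 to 10. About 92% of Day 3–4 starts go to the challenge date or earlier, and about 90% of Day 7–9 cessations go past Day 10, a mean of 13 to 15 days late (maximum 21 to 30, depending on last contact). These figures rest on equally likely assumed challenge dates; the actual cohort calendar could move them within the ranges shown.

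The scope is narrow. Only the qPCR and culture shedding time and duration endpoints are touched, and only if a swab date is partially missing. The primary vAUC already uses the scheduled day. The change is worth making because the text is wrong as written and the remedy is already in the same section, not because the trial's main conclusion depends on it.

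**What to change.** In SAP 5.3.2, remove the rules that set a missing date to the 1st, 1 January, the last day of the month or 31 December for the shedding endpoints. For start, peak, cessation and duration, use the rule already given for AUC: challenge date + scheduled day − 1, with the existing morning and evening time rule. In the example this returns 48 h, 96 h, 168 h and 120 h.

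Unscheduled swabs also count towards these endpoints and have no scheduled timepoint. For them, add that the imputed date is bounded by the adjacent dated swabs within Day 2 to 10.

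If the Note is kept, state which endpoints it covers. The cost is a few lines of SAP text and one extra line of programming for unscheduled swabs. No new data are needed.
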